6.2 Baseline Characterization

The baseline characteristics summarized for participants randomized within RGA are the same as specified in the M-SAP with the addition of ALSAQ-40 domain scores and SI, CNS-BFS total score, King's stage, weight, body mass index (BMI), serum urate concentration, serum creatinine concentration, and serum NfL concentration.

6.3 Primary Efficacy Analysis and Supportive Analyses

The primary analysis for RGA is a Bayesian shared-parameter, repeated-measures model of ALSFRS-R that accounts for loss of follow-up due to mortality. Details of the model, including documentation of operating characteristics under a range of scenarios, are provided in the "ALS Master Protocol Recommended Statistical Analysis, Design and Simulation Report" (Appendix 1 to the Master Protocol). The Bayesian shared-parameter, repeated-measures model will be applied to the FAS analysis set as the primary analysis, to the ERO analysis set as a sensitivity analysis, and to the EPP analysis set as a supportive analysis.

The estimand of the primary analysis is the relative rate of disease progression (the "disease rate ratio" or DRR) of active treatment relative to placebo in the FAS population under an assumption that active treatment slows mean time to death or death equivalent by the same proportion as treatment slows the mean rate of functional progression as measured by change in ALSFRS-R total score over time. The estimand is defined by the following attributes:

- Treatment: zilucopan administered subcutaneously once daily at a dosage of approximately 0.3 mg/kg vs. placebo.
- Population: FAS population as defined in Section 6.1.
- Variables: time to death or death equivalent and rate of change in ALSFRS-R total score from baseline to the Week 24 Visit.
- Intercurrent event 1: treatment discontinuation due to death: no ALSFRS-R data from participants who reach the death or death equivalent endpoint are included in the analysis, handled via mortality component in model, composite variable strategy approach.
- Intercurrent event 2: treatment discontinuation not due to death: handled via treatment policy approach, all data will be used including data collected during the placebo-controlled period after treatment discontinuation regardless of concomitant medication, for those participants who have not been censored due to mortality. Missing data post-treatment will not be imputed, handled via missing at random assumption.
- Population-level summary: mean ratio of hazard or progression rate of active treatment relative to placebo.

6.4 Interim Analysis

RGA will be considered for early stopping for futility according to the interim analysis schedule and definition specified in the "ALS Master Protocol Recommended Statistical Analysis, Design

and Simulation Report" (Appendix 1 to the Master Protocol). RGA will not be stopped early for success.

6.5 Secondary Efficacy Analyses

6.5.1 Hierarchical Testing

Primary inference for secondary efficacy endpoints will be based on analysis of the FAS analysis set using a repeated-measures linear mixed model for functional endpoints (see Section 6.5.2 below) and by Kaplan-Meier product-limit estimates and log-rank test for the primary survival endpoint (see Section 6.5.4 below). The sequence for testing secondary efficacy endpoints is the following:

1. HHD upper extremity percentage,
2. SVC,
3. HHD lower extremity percentage, and
4. Survival.

If the primary analysis indicates a significant slowing in disease progression from the Bayesian shared-parameter, repeated-measures model of ALSFRS-R and mortality, then each secondary efficacy endpoint in succession would be declared significant in the specified sequence using a comparison-wise criterion of two-tailed $p < 0.05$. After the first failure to declare significance, no endpoints lower in the hierarchy can be significant. This sequential closed-testing procedure controls the overall type 1 error rate at 5%. Nominal comparison-wise p-values for secondary efficacy endpoints will also be reported.

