Site Name: _____

Site Investigator: _____

Signed: _____ Date: _____

LIST OF ABBREVIATIONS

ALS	Amyotrophic Lateral Sclerosis
ALSAQ-40	Amyotrophic Lateral Sclerosis Assessment Questionnaire-40
C5	Complement component 5
CNS-BFS	Center for Neurologic Study Bulbar Function Scale
Covid-19	Coronavirus Disease 2019
FVC	Forced Vital Capacity
gMG	Generalized Myasthenia Gravis
IMNM	Immune-mediated Necrotizing Myopathy
IP	Investigational product
ITT	Intent-to-Treat
IV	Intravenous
OLE	Open Label Extension
PD	Pharmacodynamic
PK	Pharmacokinetic
RBC	Red blood cells
RSA	Regimen-Specific Appendix
SOC	Standard of care
SVC	Slow Vital Capacity
VC	Vital Capacity

REGIMEN-SPECIFIC APPENDIX SUMMARY

Regimen-Specific Appendix A

For 0.3mg/kg SC zilucoplan administered once daily and placebo

Allocation to Treatment Regimens

Participants must first be screened under the Master Protocol and before they are randomized to an RSA.

As soon as pre-defined criteria for futility for the RSA are met, or the target number of randomized participants has been reached, enrollment will stop in the RSA.

Number of Planned Participants and Treatment Groups

The number of planned participants for this regimen is approximately 160.

There are 2 treatment groups for this regimen, active and placebo. Participants will be randomized in a 3:1 ratio to active treatment or placebo (i.e., 120 active: 40 placebo).

Planned Number of Sites

Research participants will be enrolled from approximately 60 centers in the US.

Treatment Duration

The maximum duration of the placebo-controlled portion is 24 weeks.

Follow-up Duration

At the conclusion of the 24-week placebo-controlled period of the study, all participants will either schedule a 40-day follow up safety phone call and end their participation in the regimen or have the option to receive zilucoplan in the Open Label Extension phase of the study.

In the Open Label Extension, zilucoplan will be provided by Ra Pharmaceuticals, Inc. until zilucoplan is approved and available in the United States, or Ra Pharmaceuticals, Inc. terminates development of zilucoplan for ALS.

Total Planned Trial Duration

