2.5 Regimen Allocation

Participants in RGA are those determined eligible for Master Protocol-level inclusion and exclusion criteria and randomly assigned to RGA, stratified by use of riluzole, edaravone, both, or neither at the time of screening for the Master Protocol. Details of regimen assignment are described in the Platform Trial Regimen Assignment Plan.

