2.6 Treatment Allocation

Participants in RGA are randomly allocated in a 3:1 ratio to active or placebo treatment based on a pre-specified permuted-block randomization schedule, stratified by use of riluzole, edaravone, both, or neither at the time of screening for the Master Protocol.

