5.9 Survival

The primary definition of survival time is the same as described in the M-SAP with the clarification that PAV is defined as more than 22 hours per day of noninvasive or invasive mechanical ventilation for more than seven consecutive days. The date of PAV initiation, where applicable, will be imputed as the fifteenth day of a month if not specified more precisely. A secondary survival endpoint of death alone, independent of any death equivalent, is also defined.

Time at risk for the composite endpoint of death or death equivalent and time at risk for the endpoint of death alone will be measured from each participant's Baseline Visit. Time at risk will be censored at two time points: (1) at the Week 24 Visit as defined in the M-SAP, and (2) at a subsequent assessment of death or death equivalent scheduled approximately at the end of placebo-controlled follow-up of the last RGA participant. The primary analysis of survival will evaluate PAV-free survival to the Week 24 Visit time point.

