6.5.4 Survival and Time to Clinical Events

Survival and time to hospitalizations and clinical events will be analyzed in the FAS, ERO, EPP, STF, and SRO analysis sets. Survival analyses that include follow-up beyond the placebo-controlled period will be analyzed in the ERO analysis set. The summaries and analyses of time to death or death equivalent are the same as specified in the M-SAP with the addition of baseline age as an additional covariate in adjusted models, with the addition that the endpoints of time to death independent of occurrence of death equivalents and time to each of the hospitalization and clinical events will be separately analyzed using the same models, and with an additional adjusted analysis that includes baseline serum NfL level as a covariate. Analysis of time to

King's stage 4a or 4b will accommodate interval censoring between ALSFRS-R assessments and will be stratified by baseline King's stage.

Listings of all participants in the FAS, ERO, EPP, STF, and SRO analysis sets will document whether each participant had died, had reached a death equivalent endpoint, or was alive and free of a death equivalent and the study day of death, death equivalent, or last known alive and free of a death equivalent for each analysis timepoint.

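### SAP 6.5.1 names no strata for the confirmatory log-rank test of survival, although riluzole/edaravone use stratifies both randomisation steps and the other three ranked endpoints adjust for it

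*SAP*

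**What the plan says.** - **Test.** SAP 6.5.1 makes primary inference for survival in the FAS "by Kaplan-Meier product-limit estimates and log-rank test for the primary survival endpoint". No strata, covariates or regimen term are named. Survival is fourth in a fixed sequence, tested two-sided at 5%.
- **Endpoint.** SAP 5.9: "The primary analysis of survival will evaluate PAV-free survival to the Week 24 Visit time point".
- **Regimen assignment.** SAP 2.5 describes RGA participants as "randomly assigned to RGA, stratified by use of riluzole, edaravone, both, or neither at the time of screening for the Master Protocol".
- **Treatment allocation.** SAP 2.6 allocates 3:1 within RGA by permuted blocks, "stratified by use of riluzole, edaravone, both, or neither at the time of screening for the Master Protocol".
- **Controls.** SAP 6.1 adds placebo participants from regimens B, C and D to the FAS and notes that only concurrently enrolling regimens contribute.
- **Neighbouring endpoints.** HHD upper extremity, SVC and HHD lower extremity use the SAP 6.5.2 model, which adjusts for baseline riluzole use, baseline edaravone use and a random regimen intercept.
- **Detail of the survival analysis.** SAP 6.5.4: "The summaries and analyses of time to death or death equivalent are the same as specified in the M-SAP". It then adds baseline age to the adjusted models and a further adjusted analysis with serum NfL. Stratification is stated there only for time to King's stage 4a or 4b.

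**The concern.** A test normally reflects the stratification used at randomisation. Here the same factor is used at both randomisation steps, and the three endpoints ranked above survival adjust for it. On the SAP's wording, the formal survival test does not. Adjusted survival models are planned in 6.5.4, but 6.5.1 does not make them the primary inference.

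Borrowed controls make this matter more. RGA's permuted blocks balance RGA active against RGA placebo; they do not balance RGA active against placebo from B, C and D. If the background-therapy mix differed between RGA active and the pooled placebo, and that mix were prognostic for death or permanent ventilation, an unstratified comparison would carry the difference into the hazard ratio and the p-value.

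**Working it through.** **The plan's own figure.** The RSA summary plans about 160 participants at 3:1. 160 × 3/4 = 120 active and 160 × 1/4 = 40 placebo, as stated. No event count, hazard ratio or power is given for survival, so none can be checked.

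**Assumed inputs (not in the documents).**
- 40 placebo per regimen, so 4 × 40 = 160 pooled placebo against 120 active.
- Stratum shares in active (neither / riluzole only / edaravone only / both): 20 / 55 / 5 / 20%.
- Event risk to Week 24: 6% or 12% when balanced, 12% when imbalanced.
- Stratum hazards: moderate 1 / 0.75 / 0.75 / 0.5625; strong 1 / 0.5 / 0.5 / 0.25.

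**Balanced strata** (4,000 simulated trials per scenario). Two-sided size is 4.6–5.1% unstratified and 4.5–5.0% stratified. Power at a hazard ratio of 0.5 with 12% risk (about 26 events) is 37.4–37.5% unstratified and 37.3–37.9% stratified.

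**Imbalanced strata.** For a shift of d, the pooled placebo has d more in neither, d fewer in riluzole only, d/2 more in edaravone only and d/2 fewer in both. With no treatment effect, the apparent hazard ratio is approximately the ratio of mean hazards:

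HR = Σ(active share × hazard) / Σ(placebo share × hazard)

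- Active mean, moderate: 0.20 + 0.55×0.75 + 0.05×0.75 + 0.20×0.5625 = 0.7625.
- Placebo mean, moderate, d = 10 points: 0.30 + 0.45×0.75 + 0.10×0.75 + 0.15×0.5625 = 0.7969. HR = 0.7625/0.7969 = 0.96.
- Active mean, strong: 0.20 + 0.55×0.5 + 0.05×0.5 + 0.20×0.25 = 0.55.
- Placebo mean, strong, d = 15 points: 0.35 + 0.40×0.5 + 0.125×0.5 + 0.125×0.25 = 0.6438. HR = 0.55/0.6438 = 0.85.

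False rejection in favour of active (nominal 2.5%):

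| d (points) | Prognosis | Null HR | Unstratified | Stratified |
|---|---|---|---|---|
| 5 | moderate | 0.98 | 2.5% | 2.2% |
| 5 | strong | 0.95 | 3.2% | 2.3% |
| 10 | moderate | 0.96 | 3.3% | 2.5% |
| 10 | strong | 0.90 | 4.3% | 2.4% |
| 15 | moderate | 0.94 | 3.4% | 2.3% |
| 15 | strong | 0.85 | 5.3% | 2.0% |

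The Monte Carlo standard error near 2.5% is √(0.025×0.975/4000) = 0.25 points. Total two-sided rejection for the unstratified test stays at 4.8–5.8% in these rows. The main change is in how the error divides between the two directions.

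**How unusual such shifts are.** For a 20% stratum without any stratification, the standard error of the difference in share is √(0.2×0.8×(1/120+1/160)) = 4.8 points. Shifts of 10 and 15 points are then about 2.1 and 3.1 standard errors.

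**The case against.** A reader might infer that the confirmatory test is definitely a plain log-rank test. The documents do not establish that. Section 6.5.1 points to 6.5.4, which defers to the Master SAP. That document was not available, and strata named there would not conflict with 6.5.1. The R-SAP's silence is suggestive, since it does state stratification for King's stage, but it is not proof.

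A reader might also infer that pooling confounds the survival comparison. The documents do not support that either. Regimen assignment used the same four strata and only concurrently enrolling regimens contribute, so approximate balance is what the design leads one to expect. Shifts of 10 to 15 points would be uncommon, and chance is as likely to produce them against active as in its favour.

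Balance is still not assured. Regimen-specific screening follows assignment, and SAP 6.7.1 lists losses before randomisation (screen failure, timing out, withdrawal). RGA has its own vaccination and exclusion criteria. Unlike the safety set (STF), the FAS does not remove shared placebo participants known to be ineligible for RGA.

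The plan also contains checks. Section 6.5.4 repeats survival in the ERO set, where RGA's own blocks apply, and includes adjusted models. Section 6.5.11 compares controls across regimens. These would help expose an artefact, but they are not the confirmatory test.

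**Conclusion.** The point holds as a minor gap in specification. The confirmatory survival test is named without the factor that stratifies both randomisation steps, and no reason is given for treating survival differently from the three endpoints above it. The benefit of stratifying is protection against an imbalance that the design makes unlikely but does not exclude; there is no material gain in power. The sizes in the table depend wholly on the assumed control count, stratum shares, event risk and prognostic strength, and they describe only imbalance in the direction that favours active. The consequence is limited further because survival is tested only if the primary and three preceding secondary endpoints all succeed.

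**What to change.** Before data lock, state in SAP 6.5.1 and 6.5.4 that the confirmatory log-rank test is stratified by the four randomisation categories (riluzole, edaravone, both, neither), and report the unstratified test as sensitivity. Add no rule that merges strata according to observed events: a stratum without events contributes nothing to a stratified log-rank test, so merging for that reason is unnecessary and would be data-dependent. If the Master SAP already stratifies this test, cite the exact text instead.

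The cost is one added statement in the analysis code and, with few events, a negligible effect on power. Stratifying does not address other differences between regimens; the ERO analysis and the comparison of controls in 6.5.11 remain the checks for those.

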6.5.2 Repeated-measures Model

The specification of the repeated-measures linear mixed model and the primary linear contrast for estimating differences in 24-week change from baseline in a given continuous efficacy endpoint (ALSFRS-R total and domain scores, HHD upper extremity, lower extremity, and global average percentages, SVC, FVC by home spirometry, serum creatinine, serum NfL, ALSAQ-40 domain scores and SI, and CNS-BFS total score) are revised from those specified in the M-SAP to include a main effect of treatment.

The model will include fixed terms for discrete visit, treatment group, treatment group \times visit interaction, centered time since symptom onset and centered time since symptom onset \times visit interaction, centered delta-FRS and centered delta-FRS \times visit interaction, centered baseline riluzole use and centered baseline riluzole \times visit interaction, and centered baseline edaravone use and centered baseline edaravone \times visit interaction. The following equations describe the model with regimen random effects:

$$Y_{ij} = a_{k(i)} + \gamma_1 t_i + \gamma_{2,j} v_j + \boldsymbol{\gamma}'_3 \mathbf{z}_i + \gamma_{4,j} t_i v_j + \boldsymbol{\gamma}'_5 \mathbf{z}_i v_j + \epsilon_{ij} \quad (\text{eqn. 1})$$

$$a_k \sim N(0, \sigma_r^2), \epsilon_i \sim N(\mathbf{0}, \mathbf{R}), \text{Cov}(b_{k(i)}, \epsilon_{ij}) = 0$$

where Y_{ij} is a given efficacy endpoint measured in participant i at visit j , $a_{k(i)}$ is a random intercept for regimen k to which participant i was assigned, v_j is an indicator variable for visit j , \mathbf{z}_i is the vector of covariates (centered time since onset, centered delta-FRS, centered baseline riluzole use, and centered baseline edaravone use) for participant i , t_i is an indicator variable for treatment t to which participant i was assigned, γ_1 , $\gamma_{2,j}$, $\boldsymbol{\gamma}_3$, $\gamma_{4,j}$, and $\boldsymbol{\gamma}_5$ are estimated parameters

and vectors of parameters for the fixed effects, and ϵ_{ij} is the residual for participant i at visit j . The regimen-specific random effects are normally distributed with mean 0 and variance σ^2_r . The vector of residuals for a given participant are normally distributed with mean $\mathbf{0}$ and an unstructured covariance matrix \mathbf{R} . The regimen-specific random effect for a given participant and residuals for that participant are uncorrelated.

The following SAS code specifies the model:

```
proc mixed data=xxx method=reml;
  class regimen id trtrnd visit;
  model Value = trtrnd|visit
    sx2b1|visit dFRS|visit rlz|visit edv|visit / solution cl;
  random intercept / subject=regimen type=vc;
  repeated visit / subject=id type=un;
```

where `id` is a participant study identifier, `trtrnd` is the randomly assigned treatment group, `visit` is the visit identifier, `Value` is value of the efficacy endpoint being tested for a given participant at a given visit, `sx2b1` is years since ALS symptom onset centered at the sample median, `dFRS` is pre-baseline slope centered at the sample median, `rlz` is an indicator of riluzole use at baseline centered at the sample median, and `edv` is an indicator of edaravone use at baseline centered at the sample median. The primary estimate will be the treatment-dependent difference in change from baseline to the Week 24 Visit. The estimate and its 95% Wald confidence bounds will be obtained by a linear contrast of adjusted means. The following SAS code specifies the linear contrast for a regimen with one active treatment assuming an endpoint measured every 8 weeks and that the sort order for treatment group has the active group last and visits are sorted chronologically:

```
estimate "3|Act vs Plb|dWk 24" trtrnd*visit 1 0 0 -1 -1 0 0 1 / cl;
```

A significant difference in 24-week change from baseline in the direction of greater improvement or less worsening among participants randomized to active treatment would support inference of benefit from active treatment for the efficacy endpoint being tested. The estimand estimated by the primary linear contrast of the repeated-measures linear mixed model is the mean difference in 24-week change from baseline of a given continuous efficacy endpoint in the active treatment group relative to the placebo group in the FAS population. The estimand is defined by the following attributes:

- Treatment: zilucopan administered subcutaneously once daily at a dosage of approximately 0.3 mg/kg vs. placebo.
- Population: FAS population as defined in Section 6.1.
- Variables: absolute change in endpoint from baseline to the Week 24 Visit.
- Intercurrent event: treatment discontinuation: handled via treatment policy approach, all data will be used including data collected during the placebo-controlled period after treatment discontinuation. Missing data post-treatment, including data missing due to death, will not be imputed, handled via missing at random assumption.
- Population-level summary: difference in conditional means of active treatment relative to placebo.

Inference from this analysis is supportive of inference from the Bayesian shared-parameter, repeated-measures model for the primary endpoint and is the primary analysis for secondary endpoints. A separate supportive analysis will include centered baseline serum NfL level and the interaction of centered baseline serum NfL level and visit as additional covariates.

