3.0 (continued)	22 Jul 2022 (continued)	
Revision of Section 5.9 Survival to specify that time at risk begins at each participant's Baseline Visit and to specify that the date of PAV initiation, where applicable, will be imputed as the fifteenth day of a month if not specified more precisely.
 
Revision of Section 6.1 Analysis Sets to add the Efficacy Common Mode of Administration (ECM) analysis set, to remove the restriction on protocol deviations that could be considered for exclusion from the Efficacy Per-protocol (EPP) analysis set must be classified as major protocol deviations, to specify the time point at which data is excluded from the EPP analysis set in the case of time-dependent exclusions, and to specify that data from placebo participants from other regimens would not be excluded from the EPP analysis set due to non-adherence to protocol-specified dosing.
 
Revision of Section 6.2 Baseline Characterization to include ALSAQ-40 domain scores and SI.
 
Revision of Section 6.5.2 Repeated-measures Model to add a fixed term for treatment group (removing the shared-baseline assumption at the recommendation of the FDA) and to specify a separate supportive analysis that includes fixed terms for centered baseline serum NfL level, and centered baseline serum NfL level \times visit interaction.
 
Revision of Section 6.5.3 Random-slopes Model to add a fixed term for treatment group (removing the shared-baseline assumption) and to specify a separate supportive analysis that includes fixed terms for centered baseline serum NfL level, and centered baseline serum NfL level \times study month interaction.
 
Revision of Section 6.5.4 Survival and Time to Clinical Events to clarify that survival analyses that include follow-up beyond the placebo-controlled period will be analyzed in the ERO analysis set, to include baseline age as an additional covariate in adjusted models given strong prognostic value, and to specify an additional adjusted analysis that includes baseline serum NfL level as a covariate.
 
Revision of Section 6.5.5 CAFS to clarify that the primary CAFS analysis is specified in the ALS Master Protocol Recommended Statistical Analysis, Design and Simulation Report and to add two additional sets of CAFS analyses that adjust rank scores in linear models, one set that adjusts for time from ALS symptom onset, delta-FRS, baseline use of riluzole, and one set that adjusts

Version	Date	Description of Changes

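### The Week 24 contrast for HHD and SVC adjusts for four covariates but not for the endpoint's own baseline value, giving up some precision at the first three steps of the secondary hierarchy

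*SAP*

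**What the plan says.** SAP Section 6.5.1 bases inference on the secondary endpoints on the FAS, "using a repeated-measures linear mixed model for functional endpoints". The fixed sequence is HHD upper extremity, SVC, HHD lower extremity, then survival, each at two-sided 0.05, and the first failure ends testing. Section 6.5.2 confirms that this model "is the primary analysis for secondary endpoints".

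The model in Section 6.5.2 is "revised from those specified in the M-SAP to include a main effect of treatment". The version 3.0 entry in the revision history gives the reason: "removing the shared-baseline assumption at the recommendation of the FDA". Beyond treatment, visit and their interaction, the fixed effects in the SAS code are "sx2b1|visit dFRS|visit rlz|visit edv|visit / solution cl", that is, time since onset, delta-FRS, riluzole and edaravone, each with its visit interaction. The within-participant covariance is unstructured and there is a random intercept for regimen. The contrast is "trtrnd*visit 1 0 0 -1 -1 0 0 1 / cl", which is the active-arm change from baseline to Week 24 minus the placebo-arm change.

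Under Section 5.1, delta-FRS is computed from baseline ALSFRS-R and symptom duration. It carries no baseline HHD or SVC value.

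**The concern.** The shared-baseline form of the model gained precision by treating the two arms as having one baseline mean. Freeing that mean removes the gain, and nothing was put in its place. HHD and SVC are measured at baseline in every participant, and the baseline value is usually a strong predictor of the Week 24 value, yet it does not enter as a covariate.

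Two things follow. Confidence intervals for the first three secondary endpoints may be wider than necessary, and under fixed-sequence testing a miss at HHD upper extremity closes every later step, including survival. Also, if the arms differ by chance at baseline, part of that difference stays in the estimated change through regression to the mean.

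No other analysis written out in the regimen SAP fills the gap. The random-slopes model (6.5.3) also has a free treatment main effect. The NfL models add only NfL. CAFS (6.5.5) uses change from baseline. Placebo multiple imputation (6.5.8) uses the baseline value in its imputation regressions.

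**Working it through.** **Inputs.** From the documents: the model, contrast and covariates of Section 6.5.2; two-sided 0.05 (6.5.1); 120 active and 40 placebo in the regimen (Regimen-Specific Appendix summary); shared placebo from regimens B, C and D (SAP 6.1). Not in the documents, so assumed: the correlation r between baseline and Week 24 given the listed covariates; the SD ratio k (Week 24 SD over baseline SD); and 40 placebo participants in each of B, C and D, making 160 placebo in all. The plan states no power or SD for HHD or SVC, so there is no figure of its own to reproduce.

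**Step 1: what the contrast is.** Eqn. 1 was fitted by generalized least squares to simulated complete data (120 active, 160 placebo, four regimens). The contrast was 0.0096325094. Ordinary least squares on Week 24 minus baseline, with the same four covariates, also gave 0.0096325094. Adding the baseline value as a covariate gave 0.01161, a different estimator. The regimen random intercept is constant over visits, so it cancels from the current contrast.

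**Step 2: precision.** In units of baseline variance, per participant:

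- change score: 1 + k² − 2rk
- baseline-adjusted: k²(1 − r²)
- ratio, adjusted over change score: k²(1 − r²) / (1 + k² − 2rk)

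Example with r = 0.8, k = 1: 0.36 / 0.40 = 0.90.

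| r | k = 1.0 | k = 1.1 | k = 1.2 | k = 1.3 |
|---|---|---|---|---|
| 0.7 | 0.85 | 0.92 | 0.97 | 0.99 |
| 0.8 | 0.90 | 0.97 | 1.00 | 1.00 |
| 0.9 | 0.95 | 1.00 | 0.98 | 0.92 |
| 0.95 | 0.98 | 0.98 | 0.88 | 0.75 |

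Over r = 0.6 to 0.95 and k = 1.0 to 1.3 the range is 0.75 to 1.00. The ratio never exceeds 1, and it equals 1 when r·k = 1, where the regression of Week 24 on baseline has slope 1. If the current contrast had 80% power, ratios of 0.85, 0.90 and 0.95 would correspond to 86%, 84% and 82%.

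**Step 3: chance imbalance.** Given an observed baseline difference D (in baseline SDs), the expected Week 24 difference is the treatment effect plus r·k·D. The change score subtracts D, leaving a shift of (r·k − 1)·D. With k = 1 and D = 0.2:

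- r = 0.7: (0.7 − 1) × 0.2 = −0.06 SD
- r = 0.95: (0.95 − 1) × 0.2 = −0.01 SD

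For scale, the standard error of D is √(1/120 + 1/160) = 0.12 SD, so 0.2 SD is about 1.7 standard errors.

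**Step 4: the regimen intercept in a model of change.** All active participants are in this regimen, while under the assumed numbers three quarters of the placebo participants are in others. A random regimen intercept on change therefore down-weights the shared placebo. The table starts from the ratio of 0.90 (r = 0.8, k = 1) and keeps that intercept in the baseline-adjusted model:

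| Regimen SD, as a fraction of the change-score SD | Variance relative to current contrast |
|---|---|
| 0 | 0.90 |
| 0.025 | 0.93 |
| 0.05 | 1.02 |
| 0.10 | 1.26 |
| 0.20 | 1.64 |

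A regimen SD of about 0.05 already cancels the gain.

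**The case against.** The planned contrast is a standard, valid analysis. It targets the stated estimand directly, namely absolute change from baseline to Week 24, and it follows an FDA recommendation. The benefit of changing it rests wholly on assumed correlations and SD ratios, and it vanishes if the SD grows enough that r·k is near 1. Carrying the existing regimen intercept into a model of change could make precision worse. Section 6.5.9 leaves sensitivity analyses of the key secondaries to the Master SAP, which is not among the documents, so a baseline-adjusted analysis may already be planned there.

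Most of this stands, and it limits the point to efficiency. It does not remove it. The revision history records advice to drop the shared-baseline assumption; it records no advice against conditioning on baseline, which is a different step and needs no equal means. The regimen intercept is a reason to specify the adjusted model with care. A sensitivity analysis in the Master SAP would not alter the primary analysis set here, because SAP Section 1 makes the regimen SAP prevail.

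A reader might go further and infer that the contrast is wholly unadjusted, or that baseline imbalance biases it. Neither follows. Four covariates are adjusted for by visit, and with missing visits the likelihood also draws on baseline and interim values. Over randomization the estimate is unbiased, and in a given trial only the fraction (r·k − 1) of the imbalance remains.

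**Conclusion.** The point holds as an avoidable loss of efficiency in the primary analysis of HHD upper extremity, SVC and HHD lower extremity. It is not an error of validity. Baseline adjustment would give 0.75 to 1.00 of the current variance over the assumed range. With constant SD and correlation 0.7 to 0.9 the ratio is 0.85 to 0.95; with moderate SD growth it is often 0.97 or above. The 0.75 arises only at the extreme corner (r = 0.95, k = 1.3). The gain is best described as modest and possibly close to nil.

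These figures are large-sample results for complete data, with r and k assumed, and they require the adjusted model to carry no regimen intercept on change. The documents do not support a claim that the trial is underpowered for these endpoints, since they state no power for them, nor a claim that the FDA recommendation was mistaken.

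**What to change.** For HHD upper extremity, SVC and HHD lower extremity, make the primary model one of change from baseline at the post-baseline visits. Keep the planned treatment, visit, treatment by visit and covariate by visit terms and the unstructured covariance, and add the endpoint's baseline value and baseline value by visit. Take the treatment difference at Week 24 as the contrast. This leaves the arms' baseline means unconstrained, so it is compatible with the recorded reason for the revision.

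State that this model has no regimen random intercept. That matches the current contrast, from which the intercept already cancels. Examine regimen differences through the control comparisons already planned in Section 6.5.11. Retain the current contrast as a named sensitivity analysis. If the team prefers not to change the primary model, add the baseline-adjusted model as a named sensitivity analysis and say why own-baseline adjustment was left out.

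The cost is a paragraph of SAP text, a few lines of SAS and some added analysis work. The adjusted model relies on regimen-level shifts in change being negligible. Appendix Section 9.3 expects no systematic differences between controls across regimens, but says so for the primary endpoint only, so for HHD and SVC this remains an assumption to be checked.
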